#### **Protocol Summary**

**Study Compound:** BOTOX® (Botulinum Toxin Type A) purified neurotoxin complex (referred to in this protocol as BOTOX)

Phase: 2

**Study Objective:** to evaluate the safety and efficacy of a range of doses of BOTOX for the treatment of subjects with bilateral masseter muscle hypertrophy (MMH)

**Clinical Hypotheses:** BOTOX treatment of MMH has an acceptable safety profile and is more effective than placebo, as demonstrated by a change in lower facial volume

#### **Study Design**

Structure: multicenter, randomized, double-blind, placebo-controlled, up to 2-treatment, dose-escalation study

Duration: 12 months following randomization

Study Treatment Groups: BOTOX

Controls: placebo (saline)

*Dosage/Dose Regimen*: BOTOX or placebo will be administered intramuscularly to the bilateral masseter muscles (6 total injections, 3 injections/masseter). The initial BOTOX total dose will be 24 U (12 U/masseter) and the maximum BOTOX total dose will be 96 U (48 U/masseter). The planned dose escalation is as follows:

Cohort	Total Dose	Target Sample Size	Target Total Subjects/Cohort
1	24 U	40	50
1	placebo	10	
2	48 U	40	50
2	placebo	10	
2	72 U	40	50
3	placebo	10	
4	96 U	40	50
4	placebo	10	50

Each cohort will be enrolled over an approximately 2-week period. The next cohort will be enrolled following a planned independent Data Review Committee (DRC) meeting and Allergan's written notification to proceed.

For each cohort, the DRC including Allergan nonstudy team members and non-Allergan nonstudy clinicians will meet to review safety and efficacy data through day 90. The DRC will assess if the data support study retreatment of the current cohort and/or advancement to the next cohort.

Subjects who meet the following retreatment criteria at the day 180 visit will receive a second treatment:

- Allergan written notification allowing retreatment of the current cohort
- subject has marked (grade 4) or very marked (grade 5) bilateral masseter muscle hypertrophy, as assessed by the investigator using the Masseter Muscle Prominence Scale (MMPS)
- females of childbearing potential must have a negative urine pregnancy test prior to treatment

The second treatment is only allowed at the day 180 visit. Subjects will receive the same treatment as they received at the day 1 visit.

Randomization/Stratification: After completion of all baseline procedures, subjects will be randomized and enrolled in cohorts of approximately 50 subjects each. Within each cohort, subjects will be randomized 4:1 to BOTOX (N = approximately 40) or placebo (N = approximately 10). Stratification will be by baseline (day 1) MMPS grade.

#### **Study Population Characteristics**

*Number of Subjects*: Based on 4 planned cohorts, approximately 200 subjects will be enrolled at approximately 4 to 12 investigational sites. The actual number of subjects in the study will be determined by the number of cohorts and number of subjects entering each cohort. Approximately 70% of the enrolled population in each cohort will be Asian, and subjects of Asian race will be further grouped by self-identified ethnicity (Chinese, Japanese, Korean, or other).

Condition/Disease: adult subjects with marked (grade 4) or very marked (grade 5) MMH, as determined by the investigator using the MMPS

Key Inclusion Criteria:

- adult male or female, 18 (or older if legal age of adulthood is > 18 as per local regulations) to 50 years of age, inclusive, at the time of consent
- subject has marked (grade 4) or very marked (grade 5) bilateral MMH (identical grades for left and right masseter), as determined at screening and confirmed on day 1 by the investigator using the MMPS

Key Exclusion Criteria:

- any medical condition that may put the subject at increased medical risk with exposure to BOTOX including diagnosed myasthenia gravis, Eaton-Lambert syndrome, amyotrophic lateral sclerosis, or any other condition that might interfere with neuromuscular function
- prior botulinum toxin treatment of any serotype
  - o to the masseter muscle or lower face at any time or
  - $\circ$  to any other part of the body within the 6 months prior to study day 1
- history of dental or surgical procedure for lower facial shaping or masseter muscle reduction

  history of or current temporomandibular joint disorder (TMJD)

#### **Response Measures**

[figure not shown]
Efficacy:

#### **Primary**

• lower facial volume (cm³) calculated from VECTRA M3 digital photography system 3D image models

#### Secondary

• investigator's assessment of MMH using the MMPS (5 grades: 1 = minimal, 2 = mild, 3 = moderate, 4 = marked, 5 = very marked)

#### **General Statistical Methods and Types of Analyses:**

Three analysis populations will be used:

- The modified intent-to-treat (mITT) population will consist of all randomized subjects who received study treatment and had at least 1 follow-up visit. The analysis will be based on the actual treatment subjects received.
- The per-protocol (PP) population will consist of randomized subjects who have no significant deviations from the protocol. Key criteria will be determined prior to database lock.
- The safety population will consist of all subjects who are treated with at least 1 injection of study treatment.

Day 1 will be considered as baseline for all measures except for the dental examination and CT imaging, for which the screening visit will be considered baseline. The primary efficacy variable will be lower facial volume at day 90. The change from baseline in lower facial volume will be analyzed by analysis of variance (ANOVA) with treatment and baseline MMPS grade as factors to assess the response between each BOTOX dose compared with placebo.

For analysis of the mITT population, the last observation carried forward (LOCF) method will be used to impute missing values. For analysis of the PP population, observed data without imputation will be used.

For each cohort, there will be a database snapshot with key data through the day 90 visit, for the purpose of the DRC assessment. There will be a final database lock with all study data after all subjects have completed the study (final cohort day 360). Subjects' treatment assignment will remain blinded for all site personnel, study subjects, and Allergan personnel directly involved with ongoing operational activities of the clinical study, until completion of the final database lock.

Data will be summarized with descriptive statistics, frequency tables, and data listings. Categorical variables will be analyzed using Fisher's exact tests, Pearson's chi-square tests, or Cochran-Mantel-Haenszel (CMH) tests as appropriate. Continuous variables will be analyzed using t-test, analysis of covariance (ANCOVA), or corresponding nonparametric methods.

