#### 1.2 Rationale for Efficacy Assessments

In the medical literature, various imaging methods have been used to assess effects of botulinum toxin on masseter muscle size and lower facial shape (refer to the Investigator's Brochure). Technologies used to measure quantitative changes in masseter muscle volume have included ultrasound, computed tomography (CT), and magnetic resonance imaging (MRI). Photographic technologies developed to provide 3-dimensional (3D) quantitative analysis of facial morphology include image subtraction technique, moire topography, liquid crystal scanning, light luminance scanning, laser scanning, stereo-lithography, and passive stereophotogrammetry (Adriaens, 2012; Kim et al, 2005; Tzou and Frey, 2011), which all measure change to the lower facial contour. Previous studies reported peak efficacy of botulinum toxin treatment of MMH at 3 months (Hong et al, 2005; Kim et al, 2003; Kim et al, 2007; Park et al, 2003), therefore, day 90 is the primary timepoint in the present study.

In the present study, the VECTRA M3 3D Stereophotogrammetry system

and CT imaging will be used to quantify the effect of BOTOX by lower facial volume (Attachment 12.1.2) and masseter muscle volume (Attachment 12.1.3), respectively. The VECTRA system has previously been validated for use in the facial region (de Menezes, 2010), and data from this study will be used to validate its use in the defined lower facial area encompassing the masseter muscle. In addition, the lower facial width (Attachment 12.1.4) and mandibular facial angle (Attachment 12.1.5) will

be calculated using 2-dimensional (2D) images projected from the VECTRA M3 3D image models.

Allergan developed the MMPS, a clinician's assessment tool for evaluation of masseter muscle prominence associated with MMH (see Attachment 12.1.1). The MMPS is to be used by trained clinicians to evaluate and grade the hypertrophy of the masseter muscle on the left and right sides of the face. The MMPS is a static measurement encompassing both visual and palpable examination of the masseter muscle both at rest and at jaw-clench state. The MMPS showed substantial inter- and intra-rater reliability in the nontreatment scale validation Study 191622-128, confirming its acceptability for use in the present study.

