# 3 Study Design

This is a multicenter, randomized, placebo-controlled, up to 2-treatment, dose-escalation study to assess a range of doses of BOTOX for the treatment of MMH. Up to 16 scheduled

visits are planned: screening (day -56 to day -1), day 1 (randomization/treatment), day 14 (telephone followup), monthly (days 30, 60, 90, 120, 150, 180 [possible retreatment]), and day 194 (telephone followup, only for subjects retreated at day 180), monthly (days 210, 240, 270, 300, and 330), and study exit (day 360).

After completion of all baseline study procedures and re-verification that the subjects meet all inclusion and exclusion criteria, subjects will be randomized and enrolled in cohorts of approximately 50 subjects each. Within each cohort, subjects will be randomized 4:1 to BOTOX (N = approximately 40) or placebo (N = approximately 10). Stratification will be by baseline (day 1) MMPS grade. Approximately 70% of the enrolled population in each cohort will be Asian, and subjects of Asian race will be further grouped by self-identified ethnicity (Chinese, Japanese, Korean, or other). Each cohort will be enrolled over approximately a 2-week period. When at least 50 subjects have been enrolled, randomization will be halted to allow observation of the cohort through the day 90 visit. The next cohort will be enrolled following a planned independent Data Review Committee (DRC) meeting (see Section 3.1) and Allergan's written notification to proceed.

On day 1, subjects will receive a single treatment of either BOTOX or placebo administered bilaterally to the masseter muscles as 3 injections/masseter in the area of maximal muscle bulge. The initial BOTOX total dose will be 24 U (12 U/masseter) and the maximum total dose will be 96 U (48 U/masseter). Table 2 shows the planned dose-escalation scheme.

Table 2 Dose Escalation by Cohort

Cohort	Total Dose	Target Sample Size	Target Total Subjects/Cohort
1	24 U	40	50
1	placebo	10	
2.	48 U	40	50
2	placebo	10	
2	72 U	40	50
3	placebo	10	
4	96 U	40	50
4	placebo	10	50

Based on the DRC assessment and provisions for retreatment, subjects who meet the retreatment criteria (see Section 5.10) at the day 180 visit may receive a second study treatment. The second treatment is only allowed at the day 180 visit, and the same dose as day 1 will be administered.

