### **2.3.5 Handling Drop-out or Missing Data**

For efficacy analyses of mITT population of the change from baseline in lower facial volume using VECTRA 3D images, MMPS, lower facial width, mandibular facial angle, CT masseter muscle volume, LFSC, and LFSQ, last observation carried forward (LOCF) will be used to impute missing values for each scheduled visit. Only missing data for visits up to day 180 of each treatment cycle will be imputed. Missing data for visits after day 180 of each cycle will not be imputed. If a subject exited the study before day 180 of a treatment cycle, visits after the study exit will not be imputed.

Missing baseline values for lower facial width, mandibular facial angle, CT masseter muscle volume, LFSC, and LFSQ will be imputed using the average of subjects with non-missing values. Missing values for change from baseline in lower facial volume using VECTRA 3D images at day 30 will be imputed using the average of subjects with non-missing values.

For angle measurements, the average degree from both sides of the face will be determined first; if the degree of angle is missing for 1 side of the face, then the angle for the subject will be based on the angle of the other side of the face. If a subject's average is a half-degree value, it will be rounded up to an integer (eg, 30.5 degree will be rounded up to 31 degrees).

For rating an individual's MMPS score, the average of the scores from both sides of the face will be determined first; if a score is missing for 1 side of the face, then the score for the subject will be based on the score of the other side of the face. If a subject's average is a half-grade value, it will be rounded up to an integer to remain consistent with the original scale (eg, 1.50 will be rounded up to 2).

When implemented, imputation of missing values will be performed only for subjects who receive a treatment in the pertinent treatment cycle. For example, only subjects receiving the second treatment will have values imputed in treatment cycle 2; subjects who discontinued from the study during the first treatment will not have any data imputed in treatment cycle 2.

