### **5.1 Collection and Derivation of Primary Efficacy Assessments**

The primary efficacy variable, change from baseline in lower facial volume (cm^3), is calculated from VECTRA M3 digital photography system 3D image models [REDACTED]

Visit windows for all time points are specified in Section 2.2. The primary time point is day 90 of the first treatment cycle.

Between group comparisons will only be performed for each BOTOX group against the placebo group, and for each BOTOX group against the next higher dose BOTOX group.

For analysis of the mITT population, the last observation carried forward (LOCF) method will be used to impute missing values.

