### **5.2 Primary Efficacy Analyses**

Descriptive statistics for change from baseline in lower facial volume for each study visit (sample size, mean, standard deviation, median, minimum, and maximum) will be provided by treatment regimen for all scheduled visits.

The primary efficacy analysis will be based on the mITT population. Day 90 is the primary timepoint.

The following set of hypotheses will be used to compare the BOTOX groups with placebo:

- Null hypothesis: BOTOX and placebo are equally effective in changing lower facial volume at day 90.
- Alternative hypothesis: BOTOX and placebo are not equally effective in changing lower facial volume at day 90.

The change from baseline in lower facial volume at each visit will be analyzed using an ANOVA model with treatment, and baseline MMPS grade as factors. In addition, 2-sided 95% confidence intervals for the treatment differences will be provided.

Analysis will also be performed based on observed data (ie, strictly data that falls within the visit windows) for the mITT population.

Among-group comparisons for the placebo groups will be analyzed using an ANOVA model with treatment as factor to test whether they are combinable. If the difference among the placebo groups are significant, sensitivity analysis will also be done for the primary variable using an ANOVA model with treatment, cohort number (as numeric variable) and baseline MMPS grade as factors.

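### Primary LOCF rule fills a missed day 90 volume with a day 60 or day 30 value, although day 90 was chosen as the reported time of peak effect; the bias is small and conditional, but avoidable at little cost

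*Protocol*

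**What the plan says.** **Imputation rule.** The Protocol Summary and Protocol 7.2 apply LOCF to missing mITT values with no stated limit: "For analysis of the mITT population, the last observation carried forward (LOCF) method will be used to impute missing values". SAP 5.1 repeats it for the primary variable: "the last observation carried forward (LOCF) method will be used to impute missing values".

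**SAP limits.** SAP 2.3.5 applies LOCF visit by visit and adds two limits: "Only missing data for visits up to day 180 of each treatment cycle will be imputed", and "If a subject exited the study before day 180 of a treatment cycle, visits after the study exit will not be imputed". It also has a separate rule for the first visit: "Missing values for change from baseline in lower facial volume using VECTRA 3D images at day 30 will be imputed using the average", taken over those who have a value.

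**Choice of day 90.** Protocol 1.2 gives the reason: "Previous studies reported peak efficacy of botulinum toxin treatment of MMH at 3 months". Protocol 3 schedules clinic visits at days 30, 60, 90, 120, 150 and 180 before any second treatment.

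**Analysis.** Protocol 7.3.1 and SAP 5.2 fit an ANOVA with treatment and baseline MMPS grade at each visit, with 95% confidence intervals. SAP 5.2 adds: "Analysis will also be performed based on observed data (ie, strictly data that falls within the visit windows) for the mITT population". The protocol's per-protocol analysis, which used observed data, was removed by SAP Amendment 1. SAP 11 nevertheless lists no deviations from Protocol Section 7.

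**The concern.** LOCF assumes that a subject's change stays where it was at the last visit seen. The protocol's reason for choosing day 90 points the other way: if the effect peaks at about 3 months, a day 30 or day 60 value is expected to fall short of the day 90 value in a dose that works. A placebo value carried forward would be expected to change little. The filled values enter the ANOVA as if observed, so the contrast at day 90 shrinks.

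After the peak the error can go either way, depending on which visit is carried. The same rule fills days 120 to 180, and those visits are analysed too.

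What is at stake is mainly the comparison between doses. Protocol 1 gives the design of later studies as one purpose of the trial, and the SAP compares each dose with the next higher one. If missed visits are more frequent in one dose group than in another, the shrinkage differs between them.

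**Working it through.** **Plan's own figure.** Protocol 7.5 states 93% power for 40 BOTOX vs 10 placebo, effect size 1, 1-sided 0.10. The normal approximation gives 0.939 and the noncentral t (48 df) 0.936, so the figure reproduces. With placebo pooled over four cohorts (40 vs 40) at the SAP level of 0.05 2-sided, power is 0.993. The standard error of a 40 vs 40 difference is sqrt(1/40 + 1/40) = 0.224 SD.

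**Who is affected.** Under SAP 2.3.5 only subjects still in the study who miss a visit are filled. The visit table is not in the text available, so imaging at day 60 is inferred from the SAP's imputation and analysis at every scheduled visit. A subject who misses only day 90 carries day 60; one who also missed day 60 carries day 30.

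**Assumptions, because the documents give no rates or time course.**
- 5% to 20% of subjects lack day 90, half through in-study gaps and half through exit. Exits leave the denominator under the SAP, so m runs from 0.025/0.975 = 2.6% to 0.10/0.90 = 11.1%; rounded to 2.5% and 11% below.
- Effect at days 30/60/90/120/150/180 as a percentage of the day 90 effect: profile A 50/85/100/90/75/50; profile B 30/70/100/90/60/30.
- Placebo is flat, and missed visits are unrelated to outcome.

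**Day 90.** Relative loss = m(1 - f).

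| Carried visit | f (A, B) | m = 2.5% | m = 11% |
|---|---|---|---|
| Day 60 | 0.85, 0.70 | 0.4%, 0.75% | 1.65%, 3.3% |
| Day 30 | 0.50, 0.30 | 1.25%, 1.75% | 5.5%, 7.7% |

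With effect size 1 these percentages are hundredths of an SD, so the day 60 row is about 0.004 to 0.033 SD. At most that is 0.033/0.224 = 0.15 of one standard error.

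If exits were also carried, as the unlimited protocol wording implies, m would be 5% to 20%. The day 60 loss would then be 0.05 x 0.15 = 0.75% to 0.20 x 0.30 = 6%.

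**Power.** At m = 10%, f = 0.7 the effect size is 0.97; power is 0.925 (40 vs 10, 1-sided 0.10) or 0.990 (40 vs 40, 2-sided 0.05). At an extreme m = 20%, f = 0.5 the effect size is 0.90; power is 0.893 or 0.978.

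**Dose against dose.** Take two doses with the same true effect of 1, f = 0.70, and m = 2.5% in one and 11% in the other. The estimates are 1 - 0.0075 = 0.9925 and 1 - 0.033 = 0.967, a spurious difference of 0.0255 SD. If the shares are equal, equal effects stay equal.

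**Later visits.** Relative error = m(c - g)/g, where g is the true effect at the visit and c the carried effect.
- Day 150 carried to day 180: A gives m x (0.75 - 0.50)/0.50 = 0.5m, or +1.25% to +5.5%. B gives m x (0.60 - 0.30)/0.30 = m, or +2.5% to +11%.
- Day 60 carried to day 120: A gives m x (0.85 - 0.90)/0.90, or -0.1% to -0.6%. B gives m x (0.70 - 0.90)/0.90, or -0.6% to -2.4%.
- Day 30 carried to day 120: A gives m x (0.50 - 0.90)/0.90, or -1.1% to -4.9%. B gives m x (0.30 - 0.90)/0.90, or -1.7% to -7.3%.

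So the sign at late visits depends on which value is carried.

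**The case against.** The strongest case against acting has four parts.

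1. **Reach.** The SAP does not carry values past study exit, so dropouts are not filled at day 90. This stands: the point is confined to in-study gaps unless the protocol wording is followed.

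2. **Size and direction.** The day 90 shift is a fraction of one standard error and runs toward placebo, so it cannot create a false claim of superiority. This also stands.

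3. **The time course is assumed.** The protocol reports a peak at 3 months but not how far days 30 and 60 fall short. This stands, and it is why the claim must be conditional. A reader might infer that every dose is pulled down at day 90 and that duration is overstated throughout days 120 to 180. The documents do not support that. Protocol 1.1 includes 24 U to characterise the lowest threshold of effect, so that dose may have little effect to dilute. At day 120 an early carried value understates. The day 180 retreatment criterion (grade 4 or 5) is not evidence of waning either, since placebo subjects and non-responders can also meet it.

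4. **An observed-data analysis is already planned.** If missed visits are unrelated to outcome, it is unbiased at day 90 and shows the LOCF shift. This stands in part. That analysis is only additional, and the SAP does not say which result governs if they differ. It also drops the other visits of a subject without a day 90 image, so it loses information and is not protected if missing day 90 depends on earlier response.

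**Conclusion.** The point holds in a limited form and merits a change, without being critical. For subjects still in the study, the primary rule replaces a missing day 90 value with an earlier one, on a flat-effect assumption that conflicts with the protocol's reason for choosing day 90.

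If the effect builds to day 90 and placebo is flat, the loss with day 60 carried is about 0.4% to 3% of the effect. It is larger if day 30 is carried or if exits are carried as well. Near-peak values carried late, such as day 150 to day 180, would overstate the late effect if it wanes; day 30 or 60 values carried to day 120 would understate it. All sizes rest on assumed missing rates and profiles.

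A reader might take this as a threat to the comparison with placebo. It is not, because the bias is small and conservative there. What it can affect is the comparison between dose groups with different amounts of missing data, and the visit-by-visit description of effect.

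**What to change.** In Protocol 7.2 and 7.3.1 and SAP 2.3.5, 5.1 and 5.2:

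- Make the primary analysis a mixed model for repeated measures on observed volume changes at days 30 to 180 of cycle 1, using only assessments before any second injection.
- Include treatment, visit, treatment-by-visit, baseline MMPS grade and grade-by-visit, with an unstructured covariance and a named fallback structure if the model does not converge.
- Report each dose minus placebo at day 90 with its 95% confidence interval from this model, and the adjacent-dose contrasts from the same fit.
- Keep the LOCF ANOVA as a sensitivity analysis.
- Reconcile the protocol's unlimited LOCF wording with the SAP's rule on visits after study exit, and record the difference in SAP 11.

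**Cost.** Text changes and one standard model; no new visits, images or subjects. Six visits need 6 x 7/2 = 21 covariance parameters, set against about 200 planned subjects. The downside is that a fallback covariance must be specified in advance and that the model relies on missing at random.
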